#### 4.5.2 Electrocardiograms

The data for the ECG are used for safety monitoring and to identify AEs. No summaries or listings will be created.

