8.2.4 Electrocardiograms

Resting 12-lead ECGs will be recorded at screening and as clinically indicated throughout the study (see Table 1). ECGs should be obtained after the patient has been in a supine position for 5 minutes and recorded while the patient remains in that position.

In case of clinically significant ECG abnormalities, including a QT interval corrected for heart rate using Fridericia's formula (QTcF) value >470 ms, 2 additional 12-lead ECGs should be obtained over a brief period (eg, 30 minutes) to confirm the finding.

Situations in which ECG results should be reported as AEs are described in Section 8.3.7.

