9.5.2 Analysis of the secondary variables

9.5.2.1 Safety variables

Safety variables – adverse events

Total SAEs, AESIs, AEs leading to death, and AEs leading to study drug interruption or discontinuation will be summarized by Medical Dictionary for Regulatory Activities (MedDRA) by system organ class and preferred term, causality and maximum NCI CTCAE Grade. Deaths from all causes will be also summarized.

Data from all cycles of will be combined in the presentation of safety data. AEs (both in terms of MedDRA preferred term and CTCAE Grade) will be listed individually by patient.

Any AE occurring before treatment with IP will be included in the data listings but will not be included in the summary tables of AEs. Any AE occurring within 90 days of last dose of IP may be included in the AE summaries, but the majority of the AE summaries will omit the AEs observed after a patient has received further therapy for cancer. Further details will be provided in the SAP. Any AE that occurs after a patient has received further therapy for cancer (following discontinuation of IP) will be flagged in the data listings.

A separate data listing of AEs occurring more than 90 days after the last dose of IP will be produced. These events will not be included in AE summaries.

For the change from baseline summaries for vital signs, laboratory data, ECGs, and physical examination, the baseline value will be the latest result obtained prior to the first IP dose administration.

The QTcF will be derived during creation of the reporting database using the reported ECG values (RR and QT) using the following formula:

$QTcF = QT/RR^{(1/3)}$ where RR is in seconds

Corrected calcium product will be derived during creation of the reporting database using the following formula:

$Corrected\ calcium\ (mmol/L) = Total\ calcium\ (mmol/L) + ([40 - Albumin\ (G/L)] \times 0.02)$

The denominator used in laboratory summaries will include only evaluable patients, ie, those who had sufficient data to have the possibility of an abnormality, for example:

- If a CTCAE criterion involves a change from baseline, evaluable patients would have both a pre-dose and at least 1 post-dose value recorded.
- If a CTCAE criterion does not consider changes from baseline, to be evaluable, the patient need only have 1 post-dose value recorded.

The denominator in vital signs data should include only those patients with recorded data.

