#### 1.1.2 Secondary Objectives

Secondary Efficacy Objectives	Endpoints / Variables
To assess the efficacy of durvalumab treatment in terms of progression-free survival (PFS) and overall survival (OS)	Median PFS according to Response Evaluation Criteria in Solid Tumours version 1.1 (RECIST 1.1) as assessed by the Investigator  PFS12 and PFS24 according to RECIST 1.1 as assessed by the Investigator  Median OS, OS12, OS24, and OS36
To further assess the efficacy of durvalumab treatment in terms of objective response rate (ORR) and duration of response (DoR)	ORR according to RECIST 1.1 as assessed by the Investigator  DoR according to RECIST 1.1 as assessed by the Investigator
To assess the efficacy of durvalumab treatment in terms of lung cancer mortality	Lung cancer mortality

Secondary Safety Objectives	Endpoints / Variables
To further assess the safety and tolerability profile of durvalumab treatment, including all adverse events (AEs)	AEs, serious adverse events (SAEs), adverse events of special interest (AESIs), immune-mediated adverse events (imAEs), physical examinations, vital signs including blood pressure (BP) and pulse rate, respiratory rate, temperature, ECGs, and laboratory findings including clinical chemistry, haematology and urinalysis

Note: Analysis of ORR and DoR will be based upon Investigator assessment according to RECIST 1.1. Prior irradiated lesions may be considered measurable and selected as target lesions providing they fulfil the other criteria for measurability.

Note: An AESI is an AE of scientific and medical interest specific to understanding of the durvalumab. AESIs for durvalumab include, but are not limited to, events with a potential inflammatory or immune-mediated mechanism and which may require more frequent monitoring and/or interventions such as steroids, immunosuppressants and/or hormone replacement therapy.

Note: An imAE is defined as an AESI that is associated with drug exposure and is consistent with an immune-mediated mechanism of action and where there is no clear alternate etiology.

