### **3.2.2 Secondary Safety Endpoints**

The secondary safety endpoints of this study include:

- TEAEs and SAEs
- AESIs (see Section 3.2.3.2) and imAEs (see Section 3.2.3.3)
- ECG
- Vital signs including systolic blood pressure (SBP), diastolic blood pressure (DBP), pulse rate, temperature, and respiratory rate
- Laboratory data including clinical chemistry, haematology and urinalysis
- Physical Examination

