### 3.2.4 Electrocardiograms

These measurements are recorded as detailed in the study schedule (See [Appendix A](#)). If vital signs, ECG and blood draws for laboratory tests are scheduled at a visit, they will always be performed in the order: ECG, vital signs and then blood draws.

At Screening, and as clinically indicated throughout the study, ECGs should be obtained after the patient has been in a supine position for 5 minutes and recorded while the patient remains in that position. From these resting 12-lead ECGs values of the QT and RR intervals and the QT interval corrected for heart rate using Fridericia's correction (QTcF) is derived using the following formula:

- $QTcF = QT/RR^{(1/3)}$  where RR is in seconds

In case of clinically significant ECG abnormalities, 2 additional 12-lead ECGs will be performed. All three ECGs should include a value of QTcF over a brief period (eg, 30 minutes). A QTcF value >470 msec will confirm the ECG abnormality finding.

The value of QTcF will be re-derived from the values of RR and QT during the creation of the reporting database.

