  - All laboratory data, vital signs data that are recorded at unscheduled visits will be included in the summaries using the visit windows defined in Section [4.1.4.1](#).
  - The tumour measurements and PRO data should not be affected by any delays in treatment cycles/dates of start of treatment cycles as it is intended that they are only recorded at pre-scheduled time points. These data will be included in the summaries and analyses of the data using the visit windows defined in Section [4.1.4.2](#).
- All data collected including scheduled, delayed and unscheduled data will be listed in the patient data listings which are produced for all treated patients. They will be ordered by treatment/not treated, centre, WHO/ECOG PS group, patient and visit and, if relevant, timepoint when they were recorded. Patients who are included in the SAF will be flagged. Depending on the availability of the data, all data for the patients who are not treated will be listed separately. They will be ordered by centre, WHO/ECOG PS group, patient and visit and timepoint, if relevant.

- All adverse events will be coded using MedDRA and NCI CTCAE Grade and will be reported using SOC and PT, NCI CTCAE Grade, as appropriate.
- All concomitant and previous medications will be coded using WHO drug dictionary and will be reported using anatomical therapeutic chemical (ATC) classification and generic term.
- Baseline is defined as the last assessment of the variable under consideration prior to the first dose of durvalumab regardless of whether the assessment is on Day 1, Screening or unscheduled.

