## 6. CHANGES OF ANALYSIS FROM PROTOCOL

The analysis of the **CCI** testing as planned with the study protocol as exploratory objective will not be part for this analysis plan, with the option to be planned and carried out apart from this analysis in a separate addendum for this project.

The **CCI** was removed from the definition of the exploratory objectives in section 1.1.3 and is not mentioned with [8.1 Appendix A: Schedule of Assessments](#) in this analysis plan.

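### ECG is a declared secondary safety endpoint, but SAP 4.5.2 rules out any ECG summary or listing, and SAP Section 6 does not declare the departure

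*SAP*

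**What the plan says.** The SAP's analysis section for ECGs (4.5.2) consists of this: "The data for the ECG are used for safety monitoring and to identify AEs. No summaries or listings will be created".

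Other sections treat ECG as something to be reported:

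- SAP 1.1.2 includes it among the variables for the secondary safety objective: "respiratory rate, temperature, ECGs, and laboratory findings including clinical chemistry, haematology and urinalysis". Protocol Section 3 (Table 3) does the same.
- SAP 3.2.2 gives ECG its own bullet under "The secondary safety endpoints of this study include".
- SAP 3.2.4 says: "The value of QTcF will be re-derived from the values of RR and QT during the creation of the reporting database".
- SAP 4.1.1 plans descriptive summaries of safety data, overall and by performance status group, and adds: "All data collected including scheduled, delayed and unscheduled data will be listed in the patient data listings which are produced for all treated patients".
- Protocol 9.5 plans descriptive statistics for every variable. Protocol 9.5.2.1 sets a baseline rule that names ECGs: "For the change from baseline summaries for vital signs, laboratory data, ECGs, and physical examination, the baseline value will be the latest result".

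SAP Section 6, on changes from the protocol, covers one item in its readable text: "testing as planned with the study protocol as exploratory objective will not be part for this analysis plan".

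On collection, protocol 8.2.4 schedules one resting ECG at screening and further ECGs only when clinically indicated. It adds: "Situations in which ECG results should be reported as AEs are described in Section 8.3.7".

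**The concern.** An endpoint named in the objectives should produce something that a reader of the study report can look at. For ECG the plan collects tracings, derives QTcF from them, and then shows neither.

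The adverse event tables can show that an investigator judged an ECG finding to be an event. They cannot show the QTcF values, or how many patients had any ECG after starting durvalumab. Without that number, a reader cannot tell few problems from few ECGs.

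The second issue is traceability. The protocol's text implies ECG summaries and the SAP removes them. The section meant to record such changes does not say so.

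**Working it through.** No arithmetic applies, because the point rests on no sample size, rate or event count. The check sets the sections against each other.

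1. **Is ECG a declared endpoint?** Yes, in protocol Table 3, SAP 1.1.2 and SAP 3.2.2. SAP 3.2 also lists ECGs among the data by which safety will be assessed.

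2. **Do the SAP's general rules cover ECG?** Yes. In 4.1.1, summaries extend to all safety data and listings to all collected data, including unscheduled records. Every ECG after screening is taken on clinical indication, so the reference to unscheduled data matters here.

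3. **Does the SAP prepare ECG data for reporting?** Yes. SAP 3.2.4 gives the Fridericia formula and re-derives QTcF in the reporting database. No output in SAP Section 4 uses the result.

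4. **Does SAP 4.5.2 conflict with items 1 to 3?** Yes. It excludes both summaries and listings.

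5. **Does the exception clause in 4.1.1 resolve this?** No. That clause allows specific deviations, to be noted on the output concerned. Here no ECG output exists to carry the note.

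6. **Does the protocol expect ECG output?** By implication. Protocol 9.5 covers all variables, and 9.5.2.1 defines the baseline for change-from-baseline summaries and names ECGs. It specifies no particular ECG table.

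7. **Is the departure declared in Section 6?** No. The one item there is partly blacked out, but it is described as testing planned under an exploratory objective. ECG is a secondary safety variable, so the hidden words cannot refer to it.

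8. **Where do ECG findings go instead?** To adverse events. Protocol 8.2.4 refers to 8.3.7, which makes clinically relevant deteriorations in non-mandated parameters reportable even without symptoms. Protocol 8.3.6 also captures events revealed by observation. Myocarditis is an adverse event of special interest (protocol 8.3.12), and SAP 4.5.1.1 tabulates those events by category. The ECG data themselves have no route to any output.

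**The case against.** The strongest reply is that the specific rule governs the general one. SAP 4.5.2 is the dedicated ECG section, its wording is clear, and it gives a reason: the data serve monitoring and the identification of adverse events. A programmer would know what to produce. Protocol 9.4 leaves analysis details to the SAP, and 9.5.2.1 only fixes a baseline. Protocol 8.3.7 promises report summaries for laboratory tests and vital signs, and does not name ECG.

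Much of this stands. Reading 4.5.2 as the governing rule does settle which SAP sentence applies. With no scheduled post-baseline ECG, omitting by-visit tables is reasonable. What remains is that leaving details to the SAP is not the same as removing every output for a stated endpoint, and that Section 6 is silent.

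Some stronger readings are tempting, but the documents do not support them:

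- *That ECG alone among the secondary safety endpoints is denied output.* Physical examination also has no table of its own. SAP 3.2.7 sends its findings to medical history and adverse events. ECG differs in being expressly barred from listings and in having numeric values that this route cannot carry.
- *That urinalysis shows sparse data cannot be the reason for the bar.* Protocol Table 12 and SAP 1.2.1 put urinalysis on an as-indicated schedule after screening, and SAP 4.5.4 gives it a shift table. But SAP 3.2.6 describes urinalysis as collected at the start of each cycle, which could explain that table.
- *That every scheduled ECG is lost safety information.* The scheduled ECGs are screening recordings made before the first dose, so they say nothing about on-treatment safety.

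**Conclusion.** The point holds as a minor inconsistency. SAP 4.5.2 leaves a declared secondary safety endpoint, with a derived variable, without any output. This conflicts with SAP 4.1.1 and with what protocol 9.5 and 9.5.2.1 presuppose, and Section 6 does not declare it.

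A reader might infer that ECG safety signals will go unreported. The documents do not support that. Clinically relevant findings should reach the adverse event tables by the route in protocol 8.2.4, 8.3.6 and 8.3.7. This assumes that an ECG taken on clinical indication is treated as a non-mandated parameter or as an observation, since 8.3.7 does not name ECG. The primary endpoint and the efficacy results are unaffected.

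The size cannot be expressed as a number. The documents do not say how many post-baseline ECGs to expect, and no estimate is offered here.

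**What to change.** Replace the bar in SAP 4.5.2 with a patient listing of all ECGs, both screening and clinically indicated, including the derived QTcF. Flag post-baseline QTcF above 470 ms, the value protocol 8.2.4 already uses to prompt repeat tracings, and flag clinically significant abnormalities. State the number of patients with at least one post-baseline ECG.

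Add a sentence to SAP Section 6: ECG change-from-baseline summaries are not produced because no post-baseline ECG is scheduled.

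A count of flagged patients, shown as n only, is optional. It must not be presented as an incidence, because patients with a post-baseline ECG are selected by clinical indication.

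The cost is one listing and one sentence, from data already collected and a QTcF value already derived.

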#### 4.5.3 Vital Signs

Box plots of the vital signs results by visit will be presented.

#### 4.5.4 Laboratory Data

Laboratory data obtained up until the 90 days after last dose of study treatment or until the initiation of the first subsequent anti-cancer therapy following discontinuation of study treatment (whichever occurs first) will be used for reporting.

Absolute values and change from baseline for all continuous haematology and clinical chemistry laboratory parameters will be summarised by visit. If a patient does not have the baseline value of laboratory data or the value at visit, the change from baseline is considered as missing.

Shift tables for laboratory values by worst CTCAE Grade will be produced, and for specific parameters separate shift tables indicating hyper- and hypo- directionality of change will be produced. The laboratory parameters for which CTCAE Grade shift outputs will be produced are:

- Haematology: Haemoglobin, Leukocytes, Lymphocytes (absolute count), Neutrophils (absolute count), Platelets
- Clinical chemistry: Alanine transaminase (ALT), Aspartate transaminase (AST), Alkaline phosphatase (ALP), Total bilirubin, Sodium (hypo- and hyper-), Potassium (hypo- and hyper-), Glucose (hypo- and hyper-), and Creatinine

For categorical urinalysis parameters (Bilirubin, Blood, Glucose, Protein), a shift table will be produced comparing baseline value to maximum on-treatment value.

For the parameters with no CTCAE grading that are listed in the CSP the number and percentage of patients with laboratory values outside normal range will be summarized by shift tables from baseline to the post-baseline maximum and minimum value on-treatment.

#### 4.5.4.1 Liver Enzyme Elevations and Hy's Law

The following summaries (n, %) of the laboratory data will be used to identify cases of Hy's law:

- Elevated ALT, AST, and total bilirubin during the study
  - ALT  $\geq 3x - \leq 5x$ ,  $> 5x - \leq 8x$ ,  $> 8x - \leq 10x$ ,  $> 10x - \leq 20x$  and  $> 20x$  upper limit of normal (ULN) during the study
  - AST  $\geq 3x - \leq 5x$ ,  $> 5x - \leq 8x$ ,  $> 8x - \leq 10x$ ,  $> 10x - \leq 20x$  and  $> 20x$  ULN during the study
  - Total bilirubin  $\geq 2x - \leq 3x$ ,  $> 3x - \leq 5x$ ,  $> 5x$  ULN during the study
  - ALT or AST  $\geq 3x - \leq 5x$ ,  $> 5x - \leq 8x$ ,  $> 8x - \leq 10x$ ,  $> 10x - \leq 20x$  and  $> 20x$  ULN during the study
  - ALT or AST  $\geq 3x$  ULN and total bilirubin  $\geq 2x$  ULN during the study (Potential Hy's law): The onset date of ALT or AST elevation should be prior to or on the date of total bilirubin elevation

Narratives will be provided in the CSR for patients who have ALT  $\geq 3x$  ULN plus Total bilirubin  $\geq 2x$  ULN or AST  $\geq 3x$  ULN plus Total bilirubin  $\geq 2x$  ULN at any visit.

Liver biochemistry test results over time for patients with elevated ALT or AST (ie,  $\geq 3x$  ULN), and elevated Total bilirubin (ie,  $\geq 2x$  ULN) (at any time) will be plotted. Individual patient data where ALT or AST (ie,  $\geq 3x$  ULN) plus Total bilirubin (ie,  $\geq 2x$  ULN) are elevated at any time will also be listed.

Plots of post-baseline ALT and AST vs. post-baseline total bilirubin will also be produced with reference lines at  $3 \times \text{ULN}$  for ALT, AST, and  $2 \times \text{ULN}$  for Total bilirubin. In each plot, total bilirubin will be in the vertical axis.

#### 4.5.4.2 Assessment of Thyroid Function Test Results

Shift table for TSH test, baseline versus maximum value on treatment will be produced for the categories:

- Low
- Normal
- $> 1$  to  $2 \times \text{ULN}$
- $> 2 \times \text{ULN}$

The following summaries will include the number and percentage of patients who have elevated or low TSH:

- On-treatment elevated TSH > ULN
- On-treatment elevated TSH > ULN with TSH <= ULN at baseline
- On-treatment elevated TSH > ULN
  - With at least one T3 free/ T4 free < LLN
  - With all other T3 free/ T4 free >= LLN
  - With T3 free/ T4 free missing
- On-treatment low TSH < LLN
- On-treatment low TSH < LLN with TSH >= LLN at baseline
- On-treatment low TSH < LLN
  - With at least one T3 free/ T4 free > ULN
  - With all other T3 free/ T4 free <= ULN
  - With T3 free/ T4 free missing

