^d If TSH is measured within 14 days prior to Day 1 (first IP dose administration), it does not need to be repeated at Day 1.

^e Free T3 or free T4 will only be measured if TSH is abnormal or if there is a clinical suspicion of an AE related to the endocrine system.

ALT: Alanine aminotransferase; AST: Aspartate aminotransferase; IP: Investigational product; T3: Triiodothyronine; T4: Thyroxine; TSH: Thyroid-stimulating hormone; ULN: Upper limit of normal.

Table 11 Haematology

| | |
|--|--|
| Absolute neutrophil count ^a | Absolute lymphocyte count ^a |
| Haemoglobin | Platelet count |
| Total white cell count | Coagulation ^b |

^a Can be recorded as absolute counts or as percentages. Absolute counts will be calculated by Data Management if entered as percentage. Total white cell count, therefore, has to be provided.

- ^b For coagulation parameters, activated partial thromboplastin time (either as ratio or as an absolute value in seconds) and international normalised ratio are to be assessed at baseline on Day 1 and as clinically indicated.

Table 12 Urinalysis

| | |
|-----------------------|------------------|
| Bilirubin | Ketones |
| Blood | pH |
| Colour and appearance | Protein |
| Glucose | Specific gravity |

Note: Microscopy is preferred to investigate white blood cells and use the high-power field for red blood cells, dipstick can be used as well.

Note: Urinalysis should be done at baseline (screening) and then as clinically indicated.

If a patient shows an AST or ALT $\geq 3 \times$ ULN together with total bilirubin $\geq 2 \times$ ULN, refer to [Appendix E](#) for further instructions for cases of increases in liver biochemistry and evaluation of Hy's law (HL). These cases should be reported as SAEs if, after evaluation, they meet the criteria for a HL case or if any of the individual liver test parameters fulfil any of the SAE criteria.

All patients should have further chemistry profiles performed at 30 days (± 3 days), 2 months (± 1 week) and 3 months (± 1 week) after last dose of IP (see [Table 2](#)).

Any clinically significant abnormal laboratory values should be repeated as clinically indicated and recorded on the eCRF. Situations in which laboratory safety results should be reported as AEs are described in [Section 8.3.7](#).

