8.3.12 Adverse events of special interest

An AESI is one of scientific and medical interest specific to understanding of the IP and may require close monitoring and rapid communication by the Investigator to the Sponsor. An AESI may be serious or non-serious. The rapid reporting of AESIs allows ongoing surveillance of these events in order to characterize and understand them in association with the use of this IP.

AESIs for durvalumab (MEDI4736) include but are not limited to events with a potential inflammatory or immune-mediated mechanism and which may require more frequent monitoring and/or interventions such as steroids, immunosuppressants, and/or hormone replacement therapy. These AESIs are being closely monitored in clinical studies with durvalumab (MEDI4736) monotherapy and combination therapy. An imAE is defined as an AESI that is associated with drug exposure and is consistent with an immune-mediated MOA and where there is no clear alternate aetiology. Serologic, immunologic, and histologic (biopsy) data, as appropriate, should be used to support an imAE diagnosis. Appropriate efforts should be made to rule out neoplastic, infectious, metabolic, toxin, or other etiologic causes of the imAE.

If the Investigator has any questions with regard to an event being an imAE, the Investigator should promptly contact the Study Physician. AESIs may have additional clinical information collected in the eCRF.

AESI/imAEs observed with anti PD-L/PD-1 agents such as durvalumab include pneumonitis, hepatitis, diarrhea/colitis, intestinal perforation, endocrinopathies (hypo- and hyper-thyroidism, adrenal insufficiency, hypophysitis/hypopituitarism and Type 1 diabetes mellitus), nephritis, rash/dermatitis, myocarditis, myositis/polymyositis, pancreatitis and rare/less frequent imAEs including neuromuscular toxicities such as myasthenia gravis and Guillain-Barre syndrome.

Other inflammatory responses that are rare/less frequent with a potential immune-mediated etiology include, but are not limited to, pericarditis, sarcoidosis, uveitis, and other events involving the eye, skin, hematological, rheumatological events, vasculitis, non-infectious meningitis and non-infectious encephalitis. It is possible that events with an inflammatory or immune mediated mechanism could occur in nearly all organs

In addition, infusion-related reactions and hypersensitivity/anaphylactic reactions with a different underlying pharmacological aetiology are also considered AESIs.

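### The low-TSH part of the thyroid table counts patients with a low free T3/T4 together with patients whose free hormones are normal, and no other planned summary shows the two results jointly.

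*SAP*

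**What the plan says.** SAP section 4.5.4.2 plans counts and percentages of patients with elevated or low TSH. Under "On-treatment low TSH < LLN" there are three sub-rows: "With at least one T3 free/ T4 free > ULN", "With all other T3 free/ T4 free <= ULN" and "With T3 free/ T4 free missing". Under elevated TSH the cut is on the other side: "With at least one T3 free/ T4 free < LLN", then the remainder at or above LLN, then missing. The section also plans a "Shift table for TSH test, baseline versus maximum value on treatment", which uses TSH alone. It gives no rule for matching the date of the free hormone result to the date of the TSH result.

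Protocol section 8.2.1 (Table 10) makes the free hormones reflex tests: "Free T3 or free T4 will only be measured if TSH is abnormal or if there is a clinical suspicion of an AE". The suspected event has to be an endocrine one. Protocol section 8.3.12 lists "adrenal insufficiency, hypophysitis/hypopituitarism and Type 1 diabetes mellitus" among the endocrine events of special interest, and section 2.3.2.1 names hypophysitis/hypopituitarism as a durvalumab risk.

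**The concern.** A low TSH triggers the reflex test. If the free hormone then comes back low, the table records only that it was not above normal, in the same count as a patient whose free hormone was normal. A reader of the table cannot separate the two groups. The SAP does treat a low free hormone as worth its own row when TSH is elevated, so the omission is one-sided.

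This matters somewhat more than it would elsewhere because of protocol section 8.3.7. Deterioration in a mandated laboratory value is reported as an adverse event only if it meets a seriousness criterion or leads to discontinuation, and the reason given is that laboratory results will be summarised in the clinical study report. Where there are symptoms, the symptom is the reported event and the laboratory value is supporting information. Events of special interest are derived from preferred terms (SAP section 3.2.3.2), so an endocrine case recorded only as a symptom might not reach its category. The laboratory summaries are the natural cross-check, and this one merges the cell of interest.

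**Working it through.** The SAP states no figure to reproduce, and no sample size or error rate enters. The check is a complete assignment of hormone results to sub-rows.

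**Inputs.** The sub-row definitions in SAP section 4.5.4.2. Each of free T3 and free T4 is low, normal, high or missing, giving 4 × 4 = 16 combinations. If one hormone is missing, the patient is classified on the other; the SAP does not state this, so it is an assumption.

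**TSH below LLN.**
- Both missing: 1 combination.
- At least one above ULN: 16 − 3 × 3 = 7.
- The at-or-below-ULN sub-row: 16 − 7 − 1 = 8.

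Those eight divide as follows:
- Five contain a value below LLN: T3 low/T4 low, T3 low/T4 normal, T3 normal/T4 low, T3 low/T4 missing, T3 missing/T4 low.
- Three contain only normal measured values: normal/normal, normal/missing, missing/normal.

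**TSH above ULN.** At least one below LLN: 7. Remainder at or above LLN: 8. Missing: 1. Here a low hormone always has its own sub-row.

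**Sensitivity to the assumption.** If both hormones must be measured, the low-TSH at-or-below-ULN sub-row holds 2 × 2 = 4 combinations, three with a low value and one normal/normal. The mixing remains.

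**After splitting the sub-row.** 5 + 3 + 7 + 1 = 16. The above-ULN and missing sub-rows do not change.

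These are counts of combinations, not of patients; they show what is merged, not how often.

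**Does another output restore the joint view?**

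| Planned output | Low TSH crossed with low free T3/T4? |
|---|---|
| TSH shift table (SAP 4.5.4.2) | No: maximum TSH only |
| Shift tables for ungraded parameters, to maximum and minimum (SAP 4.5.4) | No: one parameter at a time; as a reflex test, free T3/T4 will probably often lack a baseline |
| Absolute values by visit (SAP 4.5.4) | No: one parameter at a time |
| Patient listings (SAP 4.1.1) | Only by reading patient by patient |
| Summaries of events of special interest (SAP 4.5.1.1) | No: reported events, not laboratory values |

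By contrast, SAP section 4.5.4.1 does cross ALT/AST with bilirubin, with an order of onset dates, for potential Hy's law.

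**Size of one case.** 1/150 = 0.7% at the maximum enrolment, 1/120 = 0.8% on the all-patient denominator of SAP Table 1, and 1/30 = 3.3% in the PS 2 cohort.

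**The case against.** The section is about thyroid function and does not claim to detect pituitary disease. Hypophysitis is handled through preferred terms, with a further review of terms before database lock (SAP section 3.2.3.2), and through investigator-identified immune-mediated events (section 3.2.3.3). Low free T3 and T4 values will appear in the minimum-value shift tables, the by-visit summaries and the listings. All of this stands, and it limits the point to one table and to the absence of a joint summary.

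A reader might infer more than the documents support:
- **That the pattern cannot be found at all.** The outputs just named contradict this.
- **That these patients are misfiled.** A patient with low TSH and low free T4 does satisfy the at-or-below-ULN condition. The row is coarse, not wrong, and the SAP does not label it mild or subclinical.
- **That every patient with a low free hormone and a low or normal TSH is lost.** With low TSH, one low and one high hormone goes to the above-ULN sub-row. With normal TSH, the patient is outside this table's scope but can appear under section 4.5.4.
- **That the hormone value may come from any visit.** The SAP is silent on matching; silence is an unspecified detail, not a demonstrated error.

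The link from low TSH with low free hormone to a pituitary cause is also general clinical knowledge, not a statement in the documents. Two of the five merged combinations have low T3 with T4 normal or missing, so the proposed row should not be read as a pituitary diagnosis.

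**Conclusion.** The point holds in limited form. The low-TSH sub-row lacks an LLN cut, so low and normal free hormones share a count, and no planned summary shows low TSH together with a low free hormone. That conclusion needs only the row definitions and survives either treatment of a single missing hormone. Its clinical relevance rests on the outside assumption that the joint pattern is informative about an event the protocol names as a risk.

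The effect is small. It concerns one descriptive secondary safety display in a study without a formal hypothesis test, and the primary endpoint is untouched. The documents give no rate; the number affected is probably a few patients at most. This is a free improvement, not a defect that threatens a conclusion.

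**What to change.** In SAP section 4.5.4.2, replace the low-TSH sub-row at or below ULN with two: (a) at least one free T3/T4 below LLN and none above ULN; (b) all measured free T3/T4 within the normal range. Label them by laboratory values only. State how a patient with one hormone missing is classified.

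Optionally, add a row for TSH within the normal range with at least one free T3/T4 below LLN, since the protocol allows testing on clinical suspicion alone.

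If hormone and TSH dates are to be matched, pre-specify a short window. A strict same-sample-date rule is not advised: the documents do not say that the reflex test uses the same draw, so such a rule could move patients with a real but later result into the missing sub-row, under elevated TSH as well.

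The cost is one extra row, or two with the option, plus a merge rule if dates are matched. No new data are needed.
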